6. GENERAL STATISTICAL CONSIDERATIONS

6.1. General Principles

This is a double-blind, placebo controlled randomized trial with a two-sided type I error rate of 0.05. Secondary hypotheses have been ordered according to relative importance. These will be described according to the appropriate summary statistics, e.g.:

- Percentages/proportions/odds ratios for categorical data. For tabular summaries of percentages/proportions, the denominator (e.g. number of subjects with non-missing data) will be displayed.
- Means, median, and range for continuous data, median for time-to-event data.

Confidence intervals will be generated; for the primary analysis, the confidence level will take into account the group-sequential design of the trial (see Section 6.6 and Section 8.1) whereas 95% confidence intervals will be generated for secondary and exploratory outcomes. For hazard ratio and odds ratio estimates, Wald confidence intervals will be used. For other efficacy outcomes (e.g. proportions), Wilson or Score confidence intervals will be used. For safety outcomes, exact (e.g., Clopper-Pearson) confidence intervals will be used.

When calculating treatment effects (e.g., differences, hazard ratios, odds ratios) and when using treatment arm as a covariate in regression modeling, the placebo + remdesivir arm will be used as the reference group. For regression modeling that uses strata variables defined in Section 6.4, the first stratum listed for each variable in that section will be used as the reference group.

For the final time-to-event analyses, the following SAS pseudocode will be used to perform stratified analyses to generate stratum-specific median time to event estimates and confidence intervals, stratum-specific Kaplan-Meier curves, and to perform the log-rank test. For any unstratified analyses, code can be used after the removal of the `strata ... ;` line.

```
proc lifetest data=dataset plots=(s);
  time TimeVariable * CensorVariable(1);
  strata StrataVariable;
  test TreatmentVariable;
run;
```

Note that the interim efficacy analyses will be performed using R. For all interim and final analyses, the software used will calculate the log rank statistic using the formula in Section 8.1.1.

To perform a stratified Cox proportional hazards model for the final analysis and generate the treatment arm hazard ratio along with its confidence interval, the following pseudocode will be used. For any unstratified analyses, code can be used after the removal of the `strata ... ;` line and strata variable in the `class` statement.

```
proc phreg data=dataset;
  class StrataVariable(ref=StrataLabel)
TreatmentVariable(ref=RemdesivirLabel);
  model TimeVariable * CensorVariable(1) = TreatmentVariable;
  strata StrataVariable;
  hazardratio TreatmentVariable / diff=ref cl=Wald;
  ods output HazardRatios = HRest;
run;
```

The following SAS pseudocode will be used to perform the final proportional odds model with treatment arm and disease severity as covariates and to generate the treatment odds ratio, p-value, and predicted probabilities of the ordinal scale levels by treatment arm and disease severity:

```
proc logistic data=dataset
  plots(only)=effect(x=ResponseVariable
    sliceby=DiseaseSeverityVariable*TreatmentVariable individual connect);
  class DiseaseSeverityVariable(param=ref ref=ModerateLabel)
    TreatmentVariable(param=ref ref=RemdesivirLabel);
  model ResponseVariable = TreatmentVariable StrataVariable;
  oddsratio TreatmentVariable;
  ods output OddsRatiosWald = ORest;
run;
```

6.2. Timing of Analyses

6.2.1. Interim analyses

A DSMB will monitor ongoing results to ensure patient well-being and safety as well as study integrity. The DSMB will be asked to recommend early termination or modification only when there is clear and substantial evidence of a treatment difference. More details about the interim analyses are described in Section 6.6.1 and Section 6.6.3 below. The summaries to be generated for the interim analysis are provided in the separate DSMB shell report.

6.2.2. Final Analyses

The final analyses of all outcomes and planned summaries/listings will be performed on the final full locked database and provided in the final report.

6.3. Analysis Populations

Summaries and analysis of safety data will be presented for the As Treated Population. Summaries and analysis of efficacy data will be presented for the modified intent-to-treat (mITT) population and As Treated population.

6.3.1. Intention-to-Treat (ITT) Population

The intention-to-treat (ITT) population includes all subjects who were randomized. ITT subjects will be classified by their randomized treatment assignment and randomized disease severity stratum (i.e. the stratum to which the subject randomized at enrollment, which is not necessarily equivalent to their baseline ordinal score if the subject was mis-stratified).

6.3.2. Modified Intention-to-Treat (mITT) and As Treated Populations

The modified intention-to-treat (mITT) population includes all subjects who were randomized. mITT subjects will be classified by their randomized treatment assignment and their baseline ordinal score, which is not necessarily equivalent to the disease severity stratum to which the subject randomized at enrollment.

The As Treated population includes all randomized subjects who received the interferon beta-1a/placebo study product, even if only one dose was administered.

For As Treated analyses of efficacy outcomes, subjects will be classified by their actual treatment assignment and their baseline ordinal score, unless otherwise specified in the table or figure shell. Note that if no subjects are administered the incorrect treatment and all subjects receive at least one dose of interferon beta-1a/placebo, the As Treated efficacy analysis will not be performed as they will be identical to the mITT analyses.

For As Treated analyses of safety outcomes, concomitant medications, and medical history, subjects will be classified by their actual treatment assignment and baseline ordinal score.

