6.1.2 Dosing and Administration

All subjects will receive remdesivir as a 200 mg intravenous (IV) loading dose on Day 1, followed by a 100 mg once-daily IV maintenance dose up to a 10-day total course while hospitalized. Enrollment may proceed for subjects who received one or two doses of remdesivir under EUA or similar mechanism prior to randomization. If subjects already received the loading dose, then start at 100 mg/day on Day 1. Any doses of remdesivir under an EUA (or similar mechanism) within 1 week of enrollment will be counted, so the maximum number of remdesivir doses given to a subject is 10 (i.e. EUA doses + doses on this trial). If one or two doses of remdesivir were administered (under EUA or similar mechanism) prior to study enrollment, this should be documented in eClinical as a concomitant medication given prior to Day 1.

For the subcutaneous interferon beta-1a / placebo component, subjects will receive either active product or placebo as follows:

- Interferon beta-1a will be administered every other day as a 44-microgram subcutaneous dose for a total of 4 doses while hospitalized
- A saline placebo will be administered every other day as a subcutaneous injection for a total of 4 doses while hospitalized

Study teams will instruct the administering nurse to use a different site for each subcutaneous injection. If there is an injection site reaction including skin that is irritated, edematous, reddened, bruised, or necrotic, the study product should not be administered into the affected area. If possible, select a unique site for each subsequent injection.

Dosing of the two medications does not need to occur at the same time.

Duration of therapy:

- IV remdesivir – up to 10 consecutive days while hospitalized (i.e., maximum of 10 total infusions pre-enrollment and during study).
- Subcutaneous (Interferon beta-1a or placebo) component – Days 1, 3, 5, and 7, while hospitalized.
- Both stop on discharge from hospital. If readmitted after discharge, see [Section 7.4](#).

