9.3 Populations for Analyses

An adjudication or review committee consisting of the DMID MO, her designees and the blinded statistical team may review endpoints, medications, deviations, and other special cases where expert opinion is requested for handling complicated cases.

The primary analysis will be based on an intention-to-treat population, including all subjects randomized. Similarly, safety analyses will be based a modified intent-to-treat population consisting of all subjects who received at least one dose of any investigational product.

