9.3. Adverse Events

For the calculation of incidence of adverse events (i.e., on a per subject basis), each subject will only be counted once and any repetitions of adverse events within a subject will be ignored; the denominator will be the number of subjects in the Treated population. All adverse events reported and treatment emergent will be reported in tables and listings; treatment emerge events are adverse events anytime following the initiation of administration with any study product (interferon beta-1a, remdesivir, or placebo). Select adverse event summaries will be replicated using the modified oxygen use scale.

An overall summary by treatment arm and disease severity of adverse events is presented that includes, but not limited to: subjects with at least one event, at least one related event, at least one SAE, at least one related SAE and at least one AE leading to early termination ([Table 53](#), [Table 54](#), [Table 55](#)).

Adverse events occurring in 5% of subjects (by MedDRA preferred term) in any treatment group will be presented ([Table 61](#), [Table 62](#), [Table 63](#)).

The proportion of subjects reporting at least one adverse event will be summarized by MedDRA system organ class and preferred term for each treatment arm, disease severity and overall. Denominators for percentages are the number of subjects in the Treated population.

The following summaries for adverse events will be presented by MedDRA system organ class, preferred term, disease severity and treatment group:

- Renal adverse events by preferred term ([Table 65](#), [Table 66](#));
- Hepatic adverse events by preferred term ([Table 67](#), [Table 68](#))
- Related adverse events by MedDRA system organ class and preferred term ([Table 69](#), [Table 70](#));
- Subject listing of non-serious adverse events ([Listing 13](#)) and listing of related adverse events ([Listing 14](#));
- Bar chart of non-serious related adverse events by severity and MedDRA system organ class ([Figure 28](#), [Figure 29](#));
- Bar chart of non-serious related adverse events by maximum severity and MedDRA system organ class ([Figure 30](#), [Figure 31](#)).

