	Did Not Receive Dose of Interferon/Placebo ^a	x	x	x	x	x	x

^a Counts are the numbers of subjects randomized to the specified treatment group with the specified baseline ordinal score.

^b Counts are the numbers of subjects who received the specified treatment with the specified baseline ordinal score.

Programming Notes:

If at least one subject received the incorrect treatment, then a footnote will be added which reads “XX subject[s] [was/were] randomized to [insert randomized treatment] but was administered [insert actual treatment]. In addition, a row under “Included in Population” and “Excluded from Population” will be added for the As Treated Population section with the label “Randomized to [insert randomized treatment] but administered [insert actual treatment].”

Table 3: Subject Disposition by Treatment Group and Baseline Ordinal Score – mITT Population

Subject Disposition	Interferon beta-1a + RDV (N=X)						Placebo + RDV (N=X)						All Subjects (N = X)					
	Baseline OS 4 (N=X)		Baseline OS 5 (N=X)		Baseline OS 6 (N=X)		Baseline OS 4 (N=X)		Baseline OS 5 (N=X)		Baseline OS 6 (N=X)		Baseline OS 4 (N=X)		Baseline OS 5 (N=X)		Baseline OS 6 (N=X)	
	n/N	%	n/N	%	n/N	%	n/N	%	n/N	%	n/N	%	n/N	%	n/N	%	n/N	%
Randomized	x/x	100	x/x	100	x/x	100	x/x	100	x/x	100	x/x	100	x/x	100	x/x	100	x/x	100
Terminated Early from Study	x/x	xx	x/x	xx	x/x	xx	x/x	xx	x/x	xx	x/x	xx	x/x	xx	x/x	xx	x/x	xx
Discharged from Hospital	x/x	xx	x/x	xx	x/x	xx	x/x	xx	x/x	xx	x/x	xx	x/x	xx	x/x	xx	x/x	xx
Died During Follow-up	x/x	xx	x/x	xx	x/x	xx	x/x	xx	x/x	xx	x/x	xx	x/x	xx	x/x	xx	x/x	xx
Completed Follow-up (Study Day 1) – Hospitalized Subjects in Study	x/x	xx	x/x	xx	x/x	xx	x/x	xx	x/x	xx	x/x	xx	x/x	xx	x/x	xx	x/x	xx
Ordinal Scale Data Available	x/x	xx	x/x	xx	x/x	xx	x/x	xx	x/x	xx	x/x	xx	x/x	xx	x/x	xx	x/x	xx
NEWS Data Scale Data Available	x/x	xx	x/x	xx	x/x	xx	x/x	xx	x/x	xx	x/x	xx	x/x	xx	x/x	xx	x/x	xx
Safety Laboratory Blood Draw	x/x	xx	x/x	xx	x/x	xx	x/x	xx	x/x	xx	x/x	xx	x/x	xx	x/x	xx	x/x	xx
OP Swab Collection	x/x	xx	x/x	xx	x/x	xx	x/x	xx	x/x	xx	x/x	xx	x/x	xx	x/x	xx	x/x	xx
PCR Assays Blood Draw	x/x	xx	x/x	xx	x/x	xx	x/x	xx	x/x	xx	x/x	xx	x/x	xx	x/x	xx	x/x	xx
Secondary Research Blood Draw	x/x	xx	x/x	xx	x/x	xx	x/x	xx	x/x	xx	x/x	xx	x/x	xx	x/x	xx	x/x	xx
Repeat for Days 3, 5, 8, 11																		
Completed Follow-up (Study Day 15) – All Subjects in Study	x/x	xx	x/x	xx	x/x	xx	x/x	xx	x/x	xx	x/x	xx	x/x	xx	x/x	xx	x/x	xx

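### The SAP's safety population requires an injection while the protocol's requires a dose of any study product, so adverse events in remdesivir-only subjects fall out of the safety summary tables

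*SAP*

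**What the plan says.** Protocol Appendix C 9.3 states that "safety analyses will be based a modified intent-to-treat population consisting of all subjects who received at least one dose of any investigational product".

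SAP 6.3 names a different set: "Summaries and analysis of safety data will be presented for the As Treated Population". SAP 6.3.2 then defines it: "The As Treated population includes all randomized subjects who received the interferon beta-1a/placebo study product, even if only one dose was administered". The Table 2 shell in SAP Appendix 1 follows that definition. The only reason it lists for exclusion from As Treated is "Did Not Receive Dose of Interferon/Placebo".

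The labels also shift. The protocol calls its any-product safety set modified intent-to-treat, whereas in the SAP "The modified intention-to-treat (mITT) population includes all subjects who were randomized".

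For timing, SAP 9.3 treats an event as treatment-emergent at any point "following the initiation of administration with any study product (interferon beta-1a, remdesivir, or placebo"). On scheduling, Protocol Appendix C 6.1.2 says: "Dosing of the two medications does not need to occur at the same time".

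**The concern.** The two documents define the safety population differently, and the SAP gives no reason for the narrower set. Its summary of changes (section 15) covers changes since SAP version 1.0 and does not mention this one.

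The SAP is also inconsistent with itself. It starts the safety clock at the first dose of any product, then drops a subject whose only product was remdesivir. Events in that subject are collected under the protocol and are treatment-emergent under SAP 9.3, yet they appear in no AE or SAE summary table. What is at stake is complete safety reporting and agreement with the protocol.

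The terminology adds to the problem. SAP 9.3 to 9.5 refer to a Treated population that is not separately defined, so programmers could build different denominators from the same text.

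**Working it through.** No sample size, power or alpha figure is in dispute, so the check compares definitions and then follows one subject through the table shells.

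**1. Which dose counts, by source**

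| Item | Source | Dose that counts |
|---|---|---|
| Safety population | Protocol App. C 9.3 | any investigational product |
| Start of AE and SAE collection | Protocol App. C 8.3.1, 8.3.5 | first study product given |
| Safety baseline | SAP 3.3.1 | any, remdesivir included |
| Time to death (safety analysis) | SAP 3.3.10 | any, remdesivir included |
| Composite safety endpoint | SAP 3.3.11 | any, remdesivir included |
| Treatment-emergent AE | SAP 9.3 | any, remdesivir included |
| Safety population | SAP 6.3, 6.3.2, Table 2 | interferon beta-1a/placebo injection only |

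The SAP safety population is the only entry that leaves remdesivir out.

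**2. Can a subject receive remdesivir and no injection?** Yes. The products may be given at different times (Protocol App. C 6.1.2). Progression to category 6 or 7 ends injections permanently (7.1.1.2) while remdesivir continues (6.3.1). The white cell and platelet holds in 6.1.4 apply to the injection alone. A subject may also stop study drug by choice. To be excluded from As Treated, the subject must receive none of the injections scheduled for Days 1, 3, 5 and 7.

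**3. Where that subject's data go**

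- *AEs, SAEs and safety laboratory results:* Tables 53–70 and 90–97 are As Treated only, so these data are not tabulated.
- *Deaths lost:* As Treated mortality Tables 72, 74, 76 and 78, the fatal-SAE rows of Tables 53–56, and composite Table 91.
- *Deaths kept:* mITT (all randomised) mortality Tables 71, 73, 75 and 77, and recovery and death Table 17. SAP 9.4 analyses mortality in both sets.
- *Listings 13–16:* the shells state no population restriction, so individual events may still be listed.
- *Disclosure:* Table 2 and Listing 1 count and identify exclusions from As Treated. As laid out, they do not separate remdesivir-only subjects from those never dosed.

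**4. Illustrative size.** The planned total is 831 / 0.90 = 923.3, stated as about 923 in SAP section 5. The remdesivir-only fraction *f* and the SAE incidence *s* are not in the documents; both are assumptions. Subjects dropped = 923 × *f*; those with an untabulated SAE = 923 × *f* × *s*, with *s* from 5% to 20%.

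| Assumed *f* | Subjects dropped | With an untabulated SAE |
|---|---|---|
| 0 | 0 | 0 |
| 0.5% | 4.6 | 0.2 to 0.9 |
| 1% | 9.2 | 0.5 to 1.8 |
| 2% | 18.5 | 0.9 to 3.7 |
| 5% | 46.2 | 2.3 to 9.2 |

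**The case against.** The best defence is that remdesivir is open-label background in both arms and the randomised question is interferon versus placebo. A set defined by exposure to the injection is then a natural safety set, and adding subjects with no interferon exposure dilutes the interferon arm. SAP 6.3.2 itself allows for the case in which every subject was injected. Tables 5 and 6 report exposure to each product in all randomised subjects, and the AE listings may still show the individual events.

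This argues well for keeping the injection-only set as a supportive analysis. It does not remove the conflict. The protocol fixed the any-product population, and the safety objective in SAP 3.1 compares the combined regimens.

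Two stronger readings are tempting and should be resisted.

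- A reader might infer that deaths of remdesivir-only subjects vanish from the safety reporting. They do not: SAP 9.4, within the safety chapter, also analyses mortality in all randomised subjects.
- A reader might infer that missing the first injection is enough for exclusion. It is not: one injection on any scheduled day qualifies. Laboratory holds are temporary. Eligibility already excludes white cells below 1500/µL and platelets below 50,000/µL, whereas the injection hold limits are 1000 and 25,000. Progression must come before any injection to cause exclusion, which makes that route narrow.

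**Conclusion.** The SAP's safety population conflicts with Protocol Appendix C 9.3 and with the SAP's own safety time origins. As written, it leaves AEs, SAEs and safety laboratory results of remdesivir-only subjects out of the summary tables. Their deaths are lost only from the As Treated outputs. That much follows from the text and rests on no assumption.

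The size is unknown. It is zero if everyone who received remdesivir was also injected; the range shown above depends entirely on assumed fractions. Because assignment to interferon or placebo is blinded, non-receipt of any injection should be roughly balanced between arms. The expected effect is therefore incomplete counting, not a biased comparison.

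A reader might also infer that the excluded subjects would be the sickest, so that event rates are understated. The documents do not support this. Deterioration before the first injection is one route to exclusion, but withdrawal and early discharge are others, and no counts are given.

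**What to change.** In SAP 6.3.2, define the safety population as all randomised subjects who received at least one dose of remdesivir, interferon beta-1a or placebo, as in Protocol Appendix C 9.3. Classify subjects by the injection actually received, or by randomised arm if none was given. Keep the injection-only set as a supportive safety analysis. Use this one defined term in place of the undefined Treated population in SAP 9.3 to 9.5. In Table 2, separate remdesivir-only subjects from those never dosed.

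As a separate drafting correction, remove from SAP 8.1.2 the rule that censors untreated subjects at randomisation in the As Treated recovery analysis, because the As Treated definition already excludes anyone not injected.

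The cost is SAP wording, one population flag and relabelled tables. The small downside is that a few subjects without interferon exposure may enter the interferon arm's safety denominator; the supportive analysis shows how much that matters.

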6.4. Covariates and Subgroups

As noted in Section 3.1, the main analysis of the key secondary efficacy outcomes will exclude subjects enrolled with a baseline ordinal score of 6. The main analyses of the remaining secondary efficacy outcomes will be performed in subgroups based on the baseline ordinal score. Analyses will be performed for the 4 or 5 (combined) subgroup separately from the 6 subgroup.

As a secondary analysis, the primary efficacy outcome will be summarized within each of the baseline ordinal score subgroups (4, 5, and 6 separately).

For subjects enrolled with a baseline ordinal score of 4 or 5, further subgroup analyses for the primary and key secondary efficacy outcomes will evaluate the treatment effect within the following subgroups:

- Geographic region:
 - US sites; Non-US sites
 - North American sites; Asian sites; European sites
- Duration of symptoms prior to randomization
 - Quartiles
 - <= 10 days; > 10 days
 - <= Median; > Median
- Race (White; Black/African American; Asian; Other)
- Comorbidities
 - None; Any
 - None, One, Two or more
 - Obese; Non-Obese
- Age (<40; 40-64; 65 and older),
- Sex (Female; Male),
- Severity of disease
 - Randomization stratification: 4 or 5 (separately) on ordinal scale.

Note: separate analyses for randomized severity will only be performed if at least one subject is erroneously randomized into the incorrect disease severity stratum.

Additionally, analyses of all remaining secondary efficacy outcomes and the time to death by Day 15/29 outcomes will evaluate the treatment effect within the following subgroups (among subjects enrolled with baseline ordinal score of 4 or 5 only):

- Duration of symptoms prior to randomization (<= Median; > Median)
- Severity of disease
 - Randomization stratification: 4 or 5 (separately) on ordinal scale.
 - Baseline ordinal score: 4 or 5 (separately) on ordinal scale.

Note: separate analyses for randomized stratum/baseline ordinal score will only be performed if at least one subject is erroneously randomized into the incorrect disease severity stratum.

There will also be a sensitivity analysis of the primary, key secondary, and mortality outcomes to evaluate the effect of concomitant therapy including experimental treatment and off-label use of marketed medications that are intended as treatment for COVID-19 and are given to patient prior to and during the study. A blinded review of the concomitant medication data will be performed by the medical monitor to identify medications that fall into any of the following categories of “Medications of Interest”:

- Antivirals
 - Protease inhibitors
 - Polymerase inhibitors
- Potential Treatments for COVID-19
 - Hydroxychloroquine/Chloroquine
 - Other
- Corticosteroids
- RAS Inhibitors
- Other anti-inflammatory drugs
 - Monoclonal Antibodies Targeting Cytokines
 - Other Biologic Therapies

Summaries of subjects who report use of the categories and subcategories of therapies/treatments will be provided. Note that after the blinded review of the medications, additional categories/sub-categories may be defined and/or categories/sub-categories may be combined.

In addition, the sensitivity analyses will consider the following categories (individually):

- Any Medication of Interest
- Hydroxychloroquine/Chloroquine
- Corticosteroids
- RAS Inhibitors

- Other Anti-Inflammatory Drugs

For the recovery analyses, subjects will be censored at the time of medication/therapy initiation. If a subject recovered prior to use of any of the medications/therapies, then the subject will still be counted as a recovery in the sensitivity analysis. For the analysis of the key secondary outcome, if a subject reports use of any of the medications/therapies prior to their Day 15 assessment, then the subject's last clinical status score prior to medication/therapy use will be used as their Day 15 outcome. For the mortality analyses, subjects will be censored at the time of medication/therapy initiation. All medication of interest sensitivity analyses will exclude subjects with a baseline ordinal score of 6.

In addition, time to recovery will be explored within the following concomitant medication use subgroups:

- Pre Enrollment Corticosteroid Use (Yes/No)
- Post Enrollment Corticosteroid Use (Yes/No)
- Post Enrollment Dexamethasone Use (Yes/No)

The effect of on-study treatment on select efficacy outcomes will also be explored among subjects who reported use of statins, angiotensin receptor blockers (ARBs), or angiotensin converting enzyme inhibitors (ACEIs) via subgroup analyses. These additional concomitant medication analyses will also exclude subjects with a baseline ordinal score of 6.

Lastly, the effect of treatment on the primary and key secondary efficacy outcomes will be explored via regression modeling controlling for age, duration of symptoms prior to randomization, baseline d-dimer, and baseline CRP values as continuous covariates. As with the above, this will exclude subjects with a baseline ordinal score of 6.

